10. EFFICACY ANALYSIS

All efficacy analyses will be performed on the ITT population.

Some supportive analyses of the primary efficacy endpoints will be performed on different populations (FAS set and PP set).

Unscheduled measurements and Visit 2 assessments done day(s) after the study treatment start date (therefore, not considered as baseline) will be excluded from the analysis and will be only listed.

Descriptive statistics for all efficacy analyses will be performed both on actually observed data and after the imputation of the missing data. The inferential analyses will be produced only after the imputation of the missing data.

Notably, for the purpose of the descriptive statistics (for both continuous and binary endpoints) after imputation of missing data, the average of the imputed and non-imputed data over the N samples will be calculated.

Details for the method of missing imputation are described in Appendix 12.1.

Individual subject listings for all data (including both observed and means of imputed values) will be provided.

10.1. Primary Efficacy Endpoints

The two co-primary efficacy endpoints are:

- Mean change in body weight from baseline over 12 weeks
- Mean change in 5-item Anorexia Symptom Subscale from baseline over 12 weeks

10.1.1. Primary efficacy endpoint derivation

The mean change effect for both co-primary endpoints will be computed as sum of the changes from baseline over 12 weeks by the time of the last assessment (either week 12 or before in case of death), and then divided by the number of assessments (observed or imputed) from baseline up to the time of the last assessment (either week 12 or before, in case of death).

For the derivation of the 5 item Anorexia Symptom Subscale FAACT A/CS domain at each visit see Section 4.3.1 and Appendix 12.3.

10.1.2. Primary efficacy analyses

The primary efficacy analyses will be conducted on the ITT set. Statistical hypothesis H_{0w} and H_{0a} , as defined in Section 7.3, will be tested using an Analysis of Variance (ANOVA) model including treatment group and the three stratification factors at randomization as categorical covariates, at a Type-I error threshold of 0.05 two-sided.

As anticipated in the beginning of this Section 10, inferential analysis will be done after imputation of missing data. An established number (N=100) of imputations will be

performed and for each of the imputation the ANOVA model will estimate treatment effect and the related standard error. The pooling of the estimates will be computed using the Rubin rule (1). The pooled effect and the related p-value will be interpreted for the primary efficacy analyses. In addition, the 95% confidence interval of the pooled difference and the least squares (LS)-mean with the 95% confidence interval will be presented per treatment group.

More details for the multiple imputation process are described in Appendix 12.1.

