The mean change effect will be computed as mean of the changes from baseline over 12 weeks by the time of the last assessment (either week 12 or before and then divided by the number of assessments (observed or imputed) from baseline up to the time of the last assessment (either week 12 or before, in case of death).

All the secondary endpoints (duration of treatment benefit and mean change from baseline) will be analyzed by means of ANOVA with explanatory variables being the randomized treatment, and the stratification factors.

The least squares (LS)-mean and 95% confidence interval will be presented per treatment group together with the LS-mean treatment effect and its 95% confidence interval. Statistics will be evaluated in each imputed datasets and pooled using Rubin's method.

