- The method of analysis (ANOVA with the 5-IASS stratum included in the ANOVA model, then including/excluding in the model the baseline covariate of the variable under analysis)

For each scenario the number of simulated studies ranged from 400 to 1000.

The simulations showed a power close to 100% to test an effect size in terms of mean change in body weight over 12 weeks approximately equal to 1.8 kg. The power to test an effect size in terms of mean change in 5-IASS over 12 weeks within the range of 1.2 - 1.4 was showed to range between 78% and 87%. This leads to a joint power for the two co-primary endpoints of at least 78%.

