8.4. Covariates

Business & Decision

Life Sciences

The three stratification factors at randomization are used as categorical covariates in each statistical model:

- Systemic anti-cancer treatment line (first line vs second line vs third or higher line)
- Cancer treatment (immunotherapy vs no immunotherapy)
- The 5-item Anorexia Symptom Subscale (≤10 vs >10).

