10.2.2. Secondary efficacy endpoints analyses

All secondary endpoints (duration of treatment benefit over 12 weeks and mean change from baseline over 12 weeks in FAACT-F 12-items, FACIT-F and FAACT total score in the secondary efficacy endpoints) will be analyzed using the same statistical model and multiple imputation approach as for the co-primary efficacy endpoints. Details are reported in Section 10.1.2 and Appendix12.1.

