10.3.2.2. Change from baseline

All the exploratory endpoints based on the "change from baseline" except the HAS and the PGIS/C will be analyzed using an ANCOVA model, with explanatory variables being the randomized treatment, the stratification factors and the baseline value.

The estimator of the effect will be the difference in change from baseline between the test group and the placebo group estimated as the difference in LS means of the ANCOVA model. The least squares (LS)-mean and 95% confidence interval will be presented per treatment group together with the LS-mean placebo-corrected treatment effect and its 95% confidence interval. Statistics will be evaluated in each imputed dataset and pooled using Rubin's method (1).

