- ANAM and placebo patients without missing data (all assessments observed)
- ANAM and placebo patients with at least 1 missing assessment imputed by the imputation process.

Note: it is theoretically possible that aberrant values are derived because of the imputation. Aberrant values are defined as follows:

- For each item of the questionnaires:
 - a) Imputed value < the lower limit (0)
 - b) Imputed value > the upper limit (4)
- \circ For the body weight:
 - a) Imputed value < the lower limit (30 Kg)
 - b) No upper limit for the Body Weight is fixed.

In the cases (a) the imputed value will be set equal to the lower value.

In the cases (b) the imputed value will be set equal to the upper value.

Unscheduled assessments of body weight and questionnaires are not considered for imputations. These values will be listed only (and have all ANL0XFLs set to blank).

 Application of Exception 1: Apply MAR (as correction to the previous control-based imputation on patients fulfilling Exception 1) *Note: Values to be imputed with MAR need first to be re-set at missing.* A flag before starting with the imputation process should identify the cases where the exception 1 should be applied. Imputed values after MAR imputation should be within the aberrant values described above for the MNAR imputation
 According to Exception 2: Impute worst value at subject level.

A flag before starting with the imputation process should identify the cases where the exception 2 should be applied. Worst value should be calculated before any imputation.

- The imputation process does not distinguish between missing due to treatment discontinuation and death. All imputed assessments after death must be set to missing.

No covariates, apart from treatment arm (as by variable or covariate, as relevant) and baseline value will be included in the MI models.

For each variable, 100 imputed values will replace each missing value.

The following variables will be separately imputed according to the above mentioned single or multiple imputation methods:

- Weight
- 5-IASS
- 4-item Anorexia Concerns Subscale (4-IACS)
- 12-item A/CS domain

Business & Decision

Life Sciences

- FAACT total score
- FACT-G total score
- FAACT TOI
- Functional Assessment of Chronic Illness Therapy-Fatigue (FACIT-F)
- FACIT-F TOI score

The PGIS and the PGIC endpoints and the hunger assessment will not be imputed.

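### The 5-IASS co-primary adjusts for baseline only as ≤10 vs >10, and the PRO mean-change secondaries omit their own baselines; some precision is lost

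*SAP*

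**What the plan says.** - **Co-primaries (SAP 10.1.2).** The hypotheses are "tested using an Analysis of Variance (ANOVA) model including treatment group and the three stratification factors at randomization as categorical covariates". SAP 8.4 makes this general: "The three stratification factors at randomization are used as categorical covariates in each statistical model". For baseline 5-IASS the factor is ≤10 vs >10.
- **Secondaries (SAP 10.2.2).** They "will be analyzed using the same statistical model and multiple imputation approach as for the co-primary efficacy endpoints". Protocol 9.4.5.3 agrees: they "will be analyzed by means of ANOVA with explanatory variables being the randomized treatment, and the stratification factors".
- **Protocol 9.4.5.1** specifies an ANOVA for the co-primaries and names no covariates.
- **Where the plan does use continuous baseline.** The exploratory by-visit changes use an "ANCOVA model, with explanatory variables being the randomized treatment, the stratification factors and the baseline value" (SAP 10.3.2.2). For imputation, SAP 12.1.1.2 says: "No covariates, apart from treatment arm (as by variable or covariate, as relevant) and baseline value will be included in the MI models".
- **Power (SAP 7.2).** The simulations used an ANOVA with the 5-IASS stratum, "then including/excluding in the model the baseline covariate of the variable under analysis". Power for a 5-IASS effect "within the range of 1.2 - 1.4 was showed to range between 78% and 87" percent. Results are not shown by model, and no reason is given for leaving the baseline value out of the final model.
- **Sensitivity and supportive analyses (SAP 10.1.3, 10.1.4).** None adds the continuous baseline. The mis-stratification analysis corrects the strata but keeps the two-level split.

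**The concern.** A change score carries baseline within it, so its variance depends on how much baseline variation the model removes. A cut at 10 removes only part. Patients scoring 1 and 9 fall in the same stratum, although they have very different room to improve or decline on a 0–20 scale.

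The loss falls on the endpoint that decides the trial. Body weight has power close to 100%, so the joint power is in effect that of 5-IASS. The sponsor had already replaced the duration-of-benefit co-primaries because corrected power for 5-IASS was 60% to 70% (protocol 1.5 and 9.2).

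The value that would recover some precision is already needed to compute the change score, so using it adds no data collection and no missingness. For FACIT-F, which shares no items with 5-IASS, the present model makes little baseline adjustment.

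**Working it through.** **Inputs from the documents.** 158 per arm, two-sided 0.05, 5-IASS effect 1.2 to 1.4, power 78% to 87% (SAP 7.2, 10.1.2).

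**Not in the documents, so assumed.** The SD of the mean change, the baseline distribution, the correlation r between baseline and the follow-up mean, and which effect goes with which power.

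**Step 1: what the stated power implies.** The 78–87% came from resampling earlier trials and cannot be reproduced without an SD. Back-solving SD = δ / [√(2/158) × (1.960 + z_power)], with √(2/158) = 0.1125:

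| Effect | SD if power is 78% (z = 0.772) | SD if power is 87% (z = 1.126) |
|---|---|---|
| 1.2 | 3.90 | 3.46 |
| 1.4 | 4.55 | 4.03 |

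**Step 2: how much baseline variation the split leaves.** Assumed baseline: a normal (mean 10, SD 4.2) rounded to whole scores and truncated to 0–17. It has SD 3.67 overall and 2.15 within strata. The split removes 1 − (2.15/3.67)² = 66% of baseline variance and leaves 34%.

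**Step 3: residual variance ratio.** Let Y be the follow-up mean with SD s, and β = r·s/3.67 its slope on baseline.

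- Stratum only: V₀ = (β − 1)² × 2.15² + s²(1 − r²), with s chosen so that V₀ equals the squared SD from step 1.
- With continuous baseline: V₁ = s²(1 − r²).
- Power with baseline = Φ(2.732/√(V₁/V₀) − 1.96), taking the present ANOVA at 78%.

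Example with effect 1.2 and r = 0.3: s = 3.785 and β = 0.309. V₁ = 13.04 and V₀ = 13.04 + 2.20 = 15.24, so the ratio is 0.855. Power = Φ(2.954 − 1.96) = 84.0%. The equivalent size is 316/0.855 = 370, or 54 more patients.

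| r | Ratio, effect 1.2 | Power | Ratio, effect 1.4 | Power |
|---|---|---|---|---|
| 0.3 | 0.855 | 84.0% | 0.912 | 81.6% |
| 0.4 | 0.905 | 81.9% | 0.950 | 80.0% |
| 0.5 | 0.951 | 80.0% | 0.981 | 78.8% |
| 0.6 | 0.987 | 78.5% | 0.999 | 78.0% |
| 0.7 | 1.000 | 78.0% | 0.990 | 78.4% |

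The gain vanishes where β is near 1, because the change score is then unrelated to baseline.

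**Step 4: allowance for imputation.** If a share L of the pooled variance is between-imputation and is not reduced, the ratio becomes L + (1 − L) × ratio. With L = 0.30 (assumed), r = 0.3 gives 82.2% (effect 1.2) and 80.5% (effect 1.4); r = 0.5 gives 79.4% and 78.5%.

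**Step 5: checks.**

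- *Simulation.* 6,000 trials per setting, ANOVA vs ANOVA plus baseline. Effect 1.2: 77.3 vs 82.4% (r = 0.3), 78.5 vs 80.4% (0.5), 78.5 vs 79.0% (0.6). Effect 1.4: 78.0 vs 81.6%, 77.3 vs 78.4%, 78.5 vs 78.6%.
- *Second parameterisation.* Let ρ be the size of the correlation between change and baseline, and q the share of baseline variance the split captures. The ratio is (1 − ρ²)/(1 − qρ²). For ρ from 0.2 to 0.6 and q of 0.60 or 0.64, the standard error falls 0.7% to 9.6% and 78% power becomes 78.6% to 85.6%.
- *Ceiling.* The SAP's scenarios span models with and without the covariate, so within them the gain cannot exceed 87 − 78 = 9 points.

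**Step 6: FACIT-F.** With equal SDs at baseline and follow-up, and c the correlation of baseline FACIT-F with the 5-IASS stratum, the ratio is (1 + r)/[(1 − r)(1 − c²) + (1 + r)]. For r from 0.3 to 0.7:

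- c = 0: 0.65 to 0.85, a variance cut of 35% to 15%.
- c = 0.4: 0.689 to 0.871, a cut of 31% to 13%.

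A/CS and FAACT total contain the 5-IASS items, so the stratum already carries part of their baseline. The variance cut for these two is not worked out here.

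**The case against.** The best case for leaving the plan alone has five parts.

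1. **This is an efficiency preference, and the gain may be nil.** Both are true. The top figure needs r = 0.3, an effect of 1.2 paired with 78%, and no between-imputation variance, in a trial that expects substantial missing data.
2. **The size rests on unseen quantities.** Also true. Nothing in SAP 7.2 ties 78% to the stratum-only model, so the gain over the planned model cannot be read from the reported range.
3. **The sponsor simulated both models.** It did, but it reports no result by model and no reason for the choice. The existence of the simulations does not support omitting the covariate.
4. **The plan is consistent by endpoint type.** SAP 10.3.2.1 analyses exploratory mean changes like the primary, and only single-visit changes use ANCOVA. So the plan does not contradict itself. It still gives the finer adjustment to exploratory endpoints and the coarser one to the confirmatory tests.
5. **The change spreads.** It would reach the sensitivity, FAS, PP and subgroup analyses, the exploratory mean changes and the mock tables. SAP 10.2.2 would also pass it to the duration endpoints unless reworded. And the three PRO secondaries come last in the testing order. These points bear on cost and drafting, not on whether the adjustment is worth making.

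**Conclusion.** The concern holds as a loss of precision, with no bias and no effect on type I error. For 5-IASS the likely gain from continuous baseline is 0 to 6 power points from a 78% start (0 to 54 patients), and near zero if r is 0.6 or more. This rests on the assumed baseline distribution (SD about 3.7), the assumed r range, and 78% being the power of the present ANOVA. The second parameterisation reaches just under 8 points at its extreme, still inside the 9-point ceiling. FACIT-F could see a variance cut of 13% to 35% under the stated assumptions. No power gain is claimed for body weight, whose power is already close to 100%. The size is uncertain, but the possible gain falls on the endpoint that limits the trial and the adjustment uses data already in hand. The change should be made. Confidence in the size is medium.

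**What to change.** Before unblinding:

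- In SAP 10.1.2, add the continuous baseline value of the variable under analysis to the co-primary models and keep the randomisation factors. This is the model already in SAP 10.3.2.2.
- In SAP 10.2.2, add it for the A/CS, FACIT-F and FAACT total mean changes only, worded so that the duration endpoints do not inherit it. Amend SAP 8.4 to match.
- For 5-IASS, state whether the ≤10/>10 stratum stays beside the continuous value. SAP 10.3.2.2 keeps it; protocol 9.4.5.4 drops it, in a sentence that refers to imputation.
- Keep the present stratified ANOVA as a supportive analysis.
- Record the change in SAP Section 13: a departure from the secondary model in protocol 9.4.5.3, and added detail beyond protocol 9.4.5.1.

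**Cost.** A SAP revision after Final v1.0: one covariate in the text and in the PROC MIXED call (Appendix 12.2.2), one Section 13 entry, and matching edits wherever the primary model is reused. No data are added. A patient without a baseline has no change score either, so no patient is lost.

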10.1.3. Sensitivity analyses

Business & Decision

Life Sciences

The sensitivity analyses are aimed to confirm robustness of the conclusion of the primary efficacy analyses but are not part of the multiplicity adjustment.

10.1.3.1. Control-based imputation

A sensitivity analysis regarding imputation of missing data will be performed using data from the placebo group only (control-based imputation) for all non-intermittent missing data. Therefore, the exceptions described in Appendix 12.1, deviating from the main control-based imputation, will not be taken into consideration.

10.1.3.2. Fluid retention replacement analysis

As fluid retention may possibly influence the weight increase, a sensitivity analysis will be performed for the primary endpoint "Mean change in body weight from baseline over 12 weeks", by considering as missing the values obtained in presence of fluid retention (for the definition of fluid retention, see Section 8.8 "Definitions").

Those missing values will be therefore imputed on the basis of the following rules for imputation:

- In case of one or more body weight assessments measured in presence of fluid retention, comprised between two assessments (pre- and post-) measured in absence of fluid retention, the lower value between the assessed weight(s) and the weight(s) estimated by the linear interpolation between pre- and postassessments will be imputed.
- If no subsequent values observed in absence of fluid retention are available, the post-baseline weight(s) recorded in presence of fluid retention will be imputed with the baseline value if that value is lower than the recorded value. Otherwise the recorded value will be used
- If fluid retention is already present at baseline (due to protocol violation), no imputation will be performed and observed values will be analyzed.

After imputation of these values, the imputation rule for the non-intermittent missing values described in Appendix 12.1 will be applied.

Furthermore, an additional sensitivity analysis will be performed for the primary endpoint "Mean change in body weight from baseline over 12 weeks", by excluding the patients for which fluid retention was reported at any time during the study.

HELSINN

T AN001 Effective Date 25 JUL 2022 Approved Version 2.00

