9.4 Statistical Analysis

9.4.1 Missing Data

A detailed presentation of missing data will be produced, indicating their amount and incidence by treatment, visit and reason (For instance: visit not done, assessment not done).

Every effort will be made to collect data from the protocol-specified assessments; patients will be asked to continue to participate in the study and complete planned visits up to the end of the treatment period (Week 24) even if they have permanently discontinued treatment with anamorelin/placebo ("retrieved drop-out" approach). Reason for treatment discontinuation will be precisely collected in the CRF and will be used to investigate possible unexpected patterns of missing data and for the imputation itself.

However, due to the nature of the patients' underlying disease, a non-ignorable amount of missing data is expected in this trial. To minimize the risk of bias in the analysis, ad hoc rules for single/multiple imputation will be adopted. The multiple imputation (MI) method for missing data, is described in the literature [Ratitch -2014; Ratitch -2013].

The missing data of the variables being part of the primary efficacy endpoints (weight, 5item Anorexia Symptom Subscale score) and the secondary/exploratory efficacy endpoints will be imputed. No imputation will be performed for survival status and no data will be imputed after patient death. All observed data will be included in the analyses, except for a sensitivity analysis in which the weight of the patients with fluid retention at the date of the assessment will be replaced with imputation approach as if they were missing.

Death from underlying disease is rather inevitable in this target population and does not reflect a failure of study treatment. According to the ICH E9(R1) guideline [ICH-1998], death is considered as an intercurrent event, after which no value is measurable. In order to measure the treatment effect for these patients, the "while alive" strategy will be used. Therefore, only values collected before death for patients dying before the endpoint will be used for the analyses.

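### In the fluid-retention sensitivity analysis, the rule for a final run of fluid-affected weights ignores the last fluid-free weight, so fluid stays in the value for patients who were already below baseline

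*SAP*

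**What the plan says.** Protocol 9.4.1 provides a sensitivity analysis in which weights of patients with fluid retention at the assessment "will be replaced with imputation approach as if they were missing". SAP 10.1.3.2 introduces the analysis in the same terms, "by considering as missing the values obtained in presence of fluid retention", and the conventions in SAP Appendix 12.1 say these values are first set to missing and then imputed.

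SAP 10.1.3.2 then gives three rules:

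- Fluid-affected weights lying between two fluid-free weights: "the lower value between the assessed weight(s) and the weight(s) estimated by the linear interpolation between pre- and postassessments will be imputed".
- Final run: "If no subsequent values observed in absence of fluid retention are available", the post-baseline weight "will be imputed with the baseline value if that value is lower than the recorded value. Otherwise the recorded value will be used".
- Fluid retention already present at baseline: observed values are analysed.

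The order of steps is also fixed: "After imputation of these values, the imputation rule for the non-intermittent missing values described in Appendix 12.1 will be applied". A companion analysis of the same endpoint is run "by excluding the patients for which fluid retention was reported at any time during the study".

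**The concern.** The analysis exists because body water can pass for weight gain; Protocol 7.2.2.1 says that it may confound the primary efficacy analysis. The final-run rule compares the recorded weight only with baseline. That works for a patient who has gained weight. It does not work for a patient who has lost tissue and then become oedematous, because the fluid hides the loss. Such a patient either keeps the recorded value or is credited with a return to baseline.

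The SAP treats comparable cases differently. The between-two-weights rule uses the patient's own fluid-free weights. The COVID-19 analysis (SAP 10.1.3.3) sends a final run of home-measured weights to the non-intermittent imputation rules as missing. A course in which oedema, ascites or effusion persists to the last visit is plausible in advanced NSCLC, so the branch could well be used. What is at stake is how far this analysis can support the weight co-primary result, not the primary test itself.

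**Working it through.** The documents state no figure for this rule, so there is none to reproduce. The check applies the rule to assumed patients.

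**Inputs.** The final-run rule is from SAP 10.1.3.2. The endpoint is from SAP 10.1.1: the sum of changes from baseline "divided by the number of assessments (observed or imputed) from baseline up to the time of the last assessment", taken here as the four visits at Weeks 3, 6, 9 and 12. All patient weights are assumed.

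**General form.** Let B be baseline, D the last fluid-free post-baseline weight, and R = D + F the recorded weight with F > 0 kg of fluid, tissue weight being held at D. The rule gives min(B, R), which exceeds D by

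min(B, D + F) - D = min(B - D, F).

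- If D < B, this is positive, so fluid stays in. When R is at or below B, all of F stays and the visit is the same as in the primary analysis.
- If D is at or above B, the value is B and the excess is B - D, zero or negative. The rule is conservative.

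**Worked patients** (baseline 50 kg; * marks a fluid-affected weight; mean change over 12 weeks in kg):

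| Patient | Recorded, Weeks 3, 6, 9, 12 | Values under SAP rule | Primary | SAP rule | Fluid-free reference | Proposed rule |
|---|---|---|---|---|---|---|
| 1 | 47, 51*, 51*, 51* | 47, 50, 50, 50 | 0.00 | -0.75 | -3.00 | -3.00 |
| 2 | 47, 49*, 49*, 49* | 47, 49, 49, 49 | -1.50 | -1.50 | -3.00 | -3.00 |
| 3 | 51, 52, 55*, 55* | 51, 52, 50, 50 | 3.25 | 0.75 | 1.75 | 0.75 |
| 4 | 51, 50.5, 51.5*, 51* | 51, 50.5, 50, 50 | 1.00 | 0.375 | -0.50 | 0.375 |

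Patient 1: (-3 + 0 + 0 + 0)/4 = -0.75, against (-3 - 3 - 3 - 3)/4 = -3.0, a gap of 2.25 kg. Patient 2: (-3 - 1 - 1 - 1)/4 = -1.5, a gap of 1.5 kg and no change from the primary analysis. For patients 1 to 3 the reference holds the last fluid-free weight. For patient 4, tissue weight is assumed to fall to 48.5 and 48 kg during the run, giving (1 + 0.5 - 1.5 - 2)/4 = -0.5. The proposed rule takes the lowest of recorded, baseline and last fluid-free post-baseline weight. It corrects patients 1 and 2, leaves patient 3 conservative, and does not correct patient 4.

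**Treatment difference.** In each arm the mean moves by (share below baseline x fluid left in) minus (share above baseline x gain removed). The shift in the difference is anamorelin's value minus placebo's. None of these shares or amounts is in the documents.

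**Knock-on in Appendix 12.1.1.2.** Take 47 kg fluid-free at Week 3, 51 kg with oedema at Week 6, then dropout. After the reset, the last value is 50: 50 - 47 is at least 0 and 50 is at least baseline, so the patient meets Exception 1 and later visits get MAR imputation. Capped at 47, the last value is below baseline, so Exception 1 fails; Exception 2 fails too, because 47 - 47 is not below 0. The patient then gets control-based imputation. A patient with fluid at every post-baseline visit, reset to 50 each time, also meets Exception 1. The appendix says the flag is set before the imputation process starts, but not whether that means before or after the fluid replacement.

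**The case against.** The companion analysis excludes every patient with reported fluid retention, so it contains none of these weights, and robustness will be judged on both analyses. That is correct and limits the harm. However, it selects on a post-randomization event and drops randomized patients, so it does not replace a sound ITT-based replacement analysis.

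Numbers may be small. SAP 13 drops the fluid-retention subgroup because of inadequate patient numbers, and exclusion criterion 6 bars edema, ascites, and effusions requiring drainage at entry. This stands. It suggests that few patients are affected, though it gives no counts.

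A reader might infer that the leftover fluid favours anamorelin and that the analysis would falsely confirm robustness. The documents do not support that. It would require the leftover fluid, net of the gain the rule removes elsewhere, to be greater on anamorelin, and no rates by arm are given. If the drug works as planned (about 1.8 kg, SAP 7.2), patients below baseline may be relatively commoner on placebo. The rule also removes real gain from patients above baseline, as patient 3 shows, and they may be commoner on anamorelin.

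The last fluid-free weight is not the truth, and part of a later rise could be tissue. That is fair; the worked gaps are measured against a reference. It is also fair that the proposed minimum still uses the recorded weight when that is lowest, so it does not literally treat the value as missing. Nor does the between-two-weights rule.

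**Conclusion.** The point holds for patients whose last fluid-free weight is below baseline. For them the final-run rule leaves in min(B - D, F) per affected visit, on the assumption that tissue weight stays at D. It conflicts with the intent stated in Protocol 9.4.1, SAP 10.1.3.2 and SAP Appendix 12.1, and with the logic of the between-two-weights rule. In the illustration, the patient-level gap is 1.5 to 2.25 kg in the 12-week mean.

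No net effect on the treatment difference can be stated in size or direction. It would also be wrong to infer a threat to the primary result: SAP 10.1.3 places sensitivity analyses outside the multiplicity adjustment, so the primary test and its alpha are unaffected. The rule should be changed because the change is cheap and the present rule does not do what the plan says.

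**What to change.** Reword the second rule in SAP 10.1.3.2: when no later fluid-free weight is available, impute the lowest of the recorded weight, the baseline weight and the last post-baseline weight recorded without fluid retention, if there is one. This never exceeds the current value and reduces to the current rule when there is no fluid-free post-baseline weight. The other two rules stay.

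Add a sentence saying that the Appendix 12.1 exception flags are set so that a reset to baseline cannot itself qualify a patient for Exception 1, for example by setting them on fluid-free observed weights only. Reconcile the introductory wording with the rules, since both replacement rules can retain a recorded value.

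The cost is a few sentences, one line of code for the rule and a check of the flag step. The sensitivity estimate may be slightly less favourable. The rule remains a conservative single-imputation convention and does not correct a decline that occurs during the fluid run (patient 4). If unblinding has already occurred, report the result as a labelled additional analysis.
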